1. INTRODUCTION

1.1 Background

Neuroendocrine malignancies refer to a diverse group of diseases that are generally rare however, their incidences are rapidly increasing. Among these, pancreatic neuroendocrine tumors (PNETs, islet cell tumor, islet cell carcinoma, or pancreatic carcinoid) account for up to 5% of all pancreatic malignancies. Functional PNET tumors make extra amounts of hormones (e.g. gastrin, insulin, and glucagon) and cause symptoms. Non-functional PNETs do not make extra amounts of hormones, and the symptoms are caused by the tumors as they grow. The majority of the non-functional tumors are malignant.

Gastrointestinal (GI) carcinoids are well-differentiated endocrine neoplasms that consist of a diverse group of tumors arising from cells of the diffuse endocrine system within the GI tract. These tumors are generally slow-growing and can be present throughout the GI tract. All GI carcinoids share common pathologic features that characterize them as well-differentiated neuroendocrine tumors (NETs) (Levy and Sobin. 2007). The World Health Organization (WHO) classification of GI NETs is clinically and prognostically useful for newly diagnosed patients with GI NETs because it accounts for specific biological behavior according to location and tumor differentiation. The specific biological behavior of a particular tumor type varies according to the cell of origin (Capella et al. 1995; Solcia et al. 2000).

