5. STUDY DESIGN

This Phase II open-label, non-randomized clinical study will be conducted by participating sites in the Sarah Cannon Research Institute network. This study will evaluate the use of carfilzomib for patients with advanced neuroendocrine tumors. For the purpose of this study, patients will receive treatment by IV infusion over 30 minutes on days 1, 2, 8, 9, 15, and 16 of each cycle. Cycles are 28 days in length. Patients will receive 20 mg/m² on Days 1 and 2 of Cycle 1. Thereafter, patients will receive 56 mg/m² on Days 8, 9, 15 and 16. Starting from Cycle 2 patients will receive 56 mg/m² on Days 1, 2, 8, 9, 15 and 16. Patients will be evaluated for response to treatment every 3 cycles; responding and/or stable patients will continue treatment, with re-evaluations every 3 cycles, unless tumor progression or intolerable toxicity occurs. Response to therapy will be assigned using RECIST v1.1criteria (see Appendix E).

The doses to be administered on specific treatment days are outlined in the table below. Patients will receive dexamethasone (4 mg for 20 mg/m² and 8 mg for 56 mg/m²) prior to receiving all carfilzomib doses in Cycle 1 and as needed throughout the study to reduce the severity of infusion reactions associated with carfilzomib. The primary endpoints for this study are ORR and PFS.

The planned enrollment for this study is 62 patients.

The study schema is presented in Figure 1.

CONFIDENTIAL

Day 1 Day 2 Day 8 Day 9 Day 15 Day 16 Day 1 Day 2 Day 8 Day 9 Day 15 Day 16

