5.2 Treatment Duration

Patients will be evaluated for toxicity at the start of each cycle. Every 3 cycles, restaging will occur with imaging, laboratory chemistries, and tumor markers as defined in Appendix D. Patients will continue on treatment until progression as defined in Appendix E or intolerance to side effects.

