10.4.1 Efficacy Analysis

Efficacy analyses will be reported for FAS population. Additionally, the ORR, Clinical Benefit Rate (CBR), and PFS will be summarized for the Evaluable Population. The following outcomes will be used to evaluate the clinical benefit of the study treatment:

- Overall Response Rate (ORR) is defined as the proportion of patients with confirmed complete response (CR) or partial response (PR (i.e. 2 CRs or PRs at least 4 weeks apart) according to RECIST v1.1 criteria.
- Clinical Benefit Rate (CBR) is defined as the proportion of patients with CR, PR or stable disease (SD) (≥ 6 cycles) according to RECIST v1.1 criteria.

CONFIDENTIAL

- For ORR and CBR, patients without a post-baseline tumor assessment will be classed as not evaluable (NE) and considered as non-responders.
- Progression-free Survival (PFS) is defined as the time from the first day of study drug administration (Day 1) to disease progression as defined by RECIST v1.1 criteria, or death on study. Patients who are alive and free from disease progression will be censored at the date of last tumor assessment.

For ORR and CBR, the estimates and the associated 95% CI based on the Clopper-Pearson method will be calculated. For PFS, Kaplan-Meier curves will be generated and the median time to event and the associated 95% CI be provided.

Safety Analysis

Safety will be assessed through the analysis of the reported incidence of treatment-emergent AEs. Treatment-emergent AEs are those with an onset on or after the initiation of therapy, and will be graded according to NCI CTCAE v4.03. A copy of CTCAE scoring system may be downloaded from: https://evs.nci.nih.gov/ftp1/CTCAE/CTCAE.

The AEs will be coded using Medical Dictionary for Regulatory Activities (MedDRA), and summarized using system organ class and preferred term for all patients in the Safety Population. In addition, summaries of serious adverse events (SAEs), AEs leading to treatment discontinuation, AEs by maximum NCI CTCAE grade, and AEs related to study treatment will also be presented.

Other safety endpoints including changes in laboratory results, vital signs and ECG findings will be summarized for the safety population. Summaries of laboratory abnormalities based on maximum CTCAE grading will also be produced.

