10.5 Analysis Time Points

10.5.1 Final Analysis

The final analysis of the study will occur when all patients progress or, for any patients with a sustained response or stable disease, a minimum of 3 treatment cycles have been completed.

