10.5.2 Planned Interim Analysis

No interim analyses are planned. Interim results may be presented at congress prior to final study report, if applicable. The design follows that of Simon et al. 1989. If < 2 of the initial 23 patients enrolled in the study fail to achieve a response, the study will be stopped and the remaining 33 additional patients will not be enrolled. Patients will be evaluated for response to treatment every 3 cycles. Patients will be removed from treatment at the time of disease progression. Patients demonstrating an extended period of stable disease will be considered non-responders after 12 cycles of treatment.

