Progressive Disease (PD):	Appearance of one or more new lesions and/or unequivocal progression of existing non-target lesions. When the subject also has measurable disease, to achieve "unequivocal progression" on the basis of the non-target disease, there must be an overall level of substantial worsening in non-target disease such that, even in presence of SD or PR in the target disease, the overall tumor burden has increased sufficiently to merit discontinuation of therapy.		

Evaluation of Best Overall Response

The best overall response is the best response recorded from the start of the treatment until disease progression/recurrence (taking as reference for PD the smallest measurements recorded since the treatment started). In general, the subject's best response assignment will depend on the achievement of both measurement and confirmation criteria.

Confirmation of response (by repeat scans after 4 weeks or as specified in the protocol) is required for studies in which response rate is the primary endpoint, but is not required in randomized studies or studies with primary survival endpoints (i.e., where response is not a primary endpoint).

CONFIDENTIAL

Target Lesions	Non-Target Lesions	New Lesions	Overall Response	
CR	CR	NO	CR	
CR	SD	NO	PR	
CR	NE	NO	PR	
PR	SD OR NE	NO	PR	
SD	SD OR NE	NO	SD	
PD	ANY	YES OR NO	PD	
ANY	PD	YES OR NO	PD	
ANY	ANY	YES	PD	

In some circumstances, it may be difficult to distinguish residual disease from normal tissue. When the evaluation of a CR depends upon this determination, it is recommended that the residual lesion be investigated by fine needle aspirate or biopsy to confirm the CR status.

When nodal disease is included in the sum of target lesions, and the nodes decrease to "normal" size (<<10 mm), they may still have a measurement reported on scans. This measurement should be recorded even though the nodes are normal in order not to overstate progression, should it be based on increase in size of the nodes. As noted earlier, this means that subjects with CR may not have a total sum of "zero" on the eCRF.

CONFIDENTIAL

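### The assessment window for the primary endpoint (ORR) is inconsistent: a first response after cycle 12 is scored in opposite ways, and Section 10.5.1 allows final analysis after only 3 cycles

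*Combined protocol and SAP*

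**What the plan says.** Five places in the protocol bear on when a response counts.

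- **Sections 10.5.2 and 12** carry the same sentence: "Patients demonstrating an extended period of stable disease will be considered non-responders after 12 cycles of treatment". In Section 12 it stands in the paragraph that names ORR as the primary outcome and sets the Primary Completion Date.
- **Section 10.4.1**: "Overall Response Rate (ORR) is defined as the proportion of patients with confirmed complete response (CR) or partial response", with confirmation at least 4 weeks apart. It gives no window and does not mention 12 cycles.
- **Appendix E**, which Section 9 makes the operative response criteria: "The best overall response is the best response recorded from the start of the treatment until disease progression/recurrence".
- **Sections 5 and 5.2**: "responding and/or stable patients will continue treatment, with re-evaluations every 3 cycles, unless tumor progression or intolerable toxicity occurs", and "Patients will continue on treatment until progression as defined in Appendix E or intolerance to side effects". Neither sets a limit at cycle 12.
- **Section 10.5.1**: the final analysis takes place when all patients have progressed or, "for any patients with a sustained response or stable disease, a minimum of 3 treatment cycles have been completed".

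No section says which of these governs a CR or PR first seen after cycle 12.

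**The concern.** The primary endpoint is a count compared with fixed cut-offs: at least 2 responses among 23 to continue, and at least 6 among 56 to reject the null (Section 10.2). Such a rule needs one definition of a response, including the period in which it may occur. Here a patient can be a responder and a non-responder at once, depending on the section followed. Because the trial is open-label and single-arm, the team would know of any late responders before having to choose.

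The 3-cycle minimum in Section 10.5.1 causes a separate difficulty. It lets the final analysis run while stable patients are far from cycle 12. It also falls before a response first seen at the cycle-3 scan could be confirmed at the next scheduled scan.

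**Working it through.** **1. The plan's own figures.** Inputs from Section 10.2: null rate 0.05, target rate 0.15, stop if 0 or 1 response in 23, reject the null if at least 6 in 56 (33 patients in stage 2). The exact rejection probability at true rate p is

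P(reject | p) = Σ over x = 2 to 23 of P[Bin(23, p) = x] × P[Bin(33, p) ≥ 6 − x].

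- p = 0.05: 0.04996, against a stated 0.05.
- p = 0.15: 0.8003, against a stated 80%.

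Both reproduce. A search for the design with the smallest expected sample size under the null also returns these boundaries.

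**2. The windows in calendar time.** From Section 5, "Cycles are 28 days in length".

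- 12 cycles × 28 days = 336 days = 48 weeks.
- 3 cycles × 28 days = 84 days = 12 weeks. The next scheduled scan follows cycle 6, at 168 days = 24 weeks. The schedule in Section 7.4 and Appendix D shows no separate confirmation scan between them.

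**3. A late responder under each rule.** Take a patient who is stable through the cycle-12 scan, has PR at cycle 15, and has it confirmed at cycle 18. The two scans are 3 × 28 = 84 days apart, so the 4-week requirement is met.

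| Passage | Scoring |
|---|---|
| Section 10.4.1 with Appendix E | Responder |
| Sections 10.5.2 and 12 | Non-responder |
| Section 10.5.1 | Analysis may already have been done |

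**4. What one such patient can change.**

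- 6/56 = 10.7% (Clopper-Pearson 95% CI 4.0 to 21.9%) rejects the null; 5/56 = 8.9% (3.0 to 19.6%) does not.
- The probability of passing stage 1 and ending on exactly 6 is Σ over x = 2 to 6 of P[Bin(23, p) = x] × P[Bin(33, p) = 6 − x]. This is 0.087 at p = 0.15 and 0.031 at p = 0.05.
- A reversal also requires at least one of those six responses to be late.

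**5. Sensitivity.** The documents do not give the share f of responses that first appear after cycle 12, so f is an assumption. Suppose that 0.05 and 0.15 are any-time rates and that the 12-cycle rule is applied. The effective rate is then p × (1 − f).

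| f | Effective target rate | Power | Type I error (true any-time rate 0.05) |
|---|---|---|---|
| 0 | 0.150 | 0.800 | 0.050 |
| 5% | 0.1425 | 0.761 | 0.041 |
| 10% | 0.135 | 0.715 | 0.033 |
| 20% | 0.120 | 0.607 | 0.020 |

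If 0.15 is instead the rate by cycle 12, power under the 12-cycle rule stays at 0.800.

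**The case against.** The strongest reply is that nothing truly conflicts. Section 10.4.1 is silent on timing and does not say that a response counts at any time. The 12-cycle sentence is specific, appears twice, and in Section 12 stands beside the primary outcome, so it can be read as limiting the general definition. Appendix E is generic RECIST text. This may well be what the sponsor intended. But no section says so, and Section 9 adopts Appendix E, whose window runs to progression. For a first response after cycle 12, the stated rules therefore give opposite answers.

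Three further replies stand:

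- **Few patients.** Only patients still free of progression after 48 weeks who then shrink enough for a PR are affected. The documents give no sign of how many there would be.
- **Conditional loss.** The power figures depend on an assumed f and on 15% being an any-time rate.
- **Disease course.** A reader might infer that late shrinkage is to be expected because the protocol describes slow growth. The sentence, "These tumors are generally slow-growing and can be present throughout the GI tract", is about gastrointestinal carcinoids. It does not cover pancreatic or every other eligible tumour, and it says nothing about late response.

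A reader might also infer that the two Simon stages are to be counted by different rules, since Section 10.5.2 puts the sentence next to the stage-1 gate. The documents do not support that: Section 12 applies the same sentence to the trial-level outcome, and no section gives the stages separate definitions.

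**Conclusion.** The ORR window is inconsistent across Sections 10.4.1, 10.5.1, 10.5.2, 12 and Appendix E, and it should be settled before any response count is made. The severity is moderate. The sample size, the boundaries and the stated error rates are correct and do not change.

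The size cannot be fixed from the documents. The range 0.761 to 0.607 holds only for f between 5% and 20% and for a 15% any-time target. A reader might infer an inflated false-positive rate; on the same assumptions, scoring by the 12-cycle rule lowers type I error (0.033 at f = 10%). A reversal from 6/56 to 5/56 is possible, but it needs a result exactly on the boundary that includes a late responder. What remains is an undefined scoring rule for the primary endpoint that could be chosen with the results in view.

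**What to change.** State one ORR window in Section 10.4.1 and use it for both Simon stages.

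- **Simplest, in line with Sections 10.5.2 and 12:** a responder has CR or PR first documented by the cycle-12 assessment and confirmed at least 4 weeks later. Later first responses are listed descriptively and do not count toward the Simon rule.
- **Alternative:** any-time best response, with the 12-cycle sentence deleted from Sections 10.5.2 and 12.

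Then align Sections 10.5.1, 10.5.2, 12 and Appendix E. In Section 10.5.1, the final ORR analysis should wait until every patient has a confirmed response, has progressed or left the study, or has completed the stated window including confirmation.

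The change is wording only. It concerns endpoint scoring and does not alter treatment duration. The cost is mainly time. Under the 12-cycle option a stage-1 no-go, or the final count, may have to wait up to 48 weeks from the last relevant patient's start. Confirmation adds at least 4 weeks (48 + 4 = 52), or 12 weeks if it relies on the scheduled cycle-15 scan (48 + 12 = 60). The sponsor should check this against the 24-month total duration in the Synopsis. Under the same option, late responses no longer contribute to the go/no-go decision.

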10.5.3 Efficacy Review

Not applicable.

CONFIDENTIAL

11. SAFETY REPORTING AND ANALYSES

Safety assessments will consist of monitoring and recording protocol-defined AEs and SAEs, measurement of protocol-specified hematology, clinical chemistry, and other protocol-specified tests that are deemed critical to the safety evaluation of the study drug.

The Principal Investigator is responsible for recognizing and reporting AEs to the SCRI Innovations Safety Department (SCRI Innovations SD) (see Section 11.1.5). It is SCRI Innovations SD's responsibility to report relevant SAEs to the applicable local or national regulatory bodies. In addition, Investigators must report SAEs and follow-up information to their responsible IRB according to the policies of that IRB.

The Principal Investigator is also responsible for ensuring that every staff member involved in the study is familiar with the content of this section.

11.1 Definitions

11.1.1 Adverse Events

Adverse event means any untoward medical occurrence associated with the use of a drug in humans, whether or not considered drug related. An adverse event (also known as adverse experience) can be any unfavorable and unintended sign (e.g., an abnormal laboratory finding), symptom, or disease temporarily associated with the use of a drug, without any judgement about causality. An adverse event can arise with any use of the drug (e.g., off-label use, use in combination with another drug) and with any route of administration, formulation, dose or including overdose.

11.1.2 Serious Adverse Event

An AE or a suspected adverse reaction (SAR) is considered "serious" if it results in any of the following outcomes:

- Death
- A life-threatening AE, defined as any adverse experience that places the subject, in the view of the Investigator, at immediate risk of death at the time of occurrence; i.e., it does not include a reaction that, had it occurred in a more severe form, might have caused death.
- Inpatient hospitalization of at least 24-hours or prolongation of existing hospitalization
- A persistent or significant incapacity or substantial disruption of the ability to conduct normal life functions
- A congenital anomaly/birth defect

Important medical events that may not result in death, be life-threatening, or require hospitalization may be considered serious when, based upon appropriate medical judgment, they may jeopardize the patient or subject and may require medical or surgical intervention to prevent one of the outcomes listed in this definition. Examples of such medical events include allergic bronchospasm requiring intensive treatment in an emergency room or at home, blood dyscrasias *CONFIDENTIAL*

STUDY DRUG(S): CARFILZOMIB AMENDMENT 2 DATE: 25 FEBRUARY 2015

or convulsions that do not result in hospitalization, or development of drug dependency or drug abuse.

It is important to distinguish between "serious" and "severe" AE, as the terms are not synonymous. Severity is a measure of intensity; however, an AE of severe intensity need not necessarily be considered serious. Seriousness serves as the guide for defining regulatory reporting obligations. "Serious" is a regulatory definition and is based on patient/event outcome or action usually associated with events that pose a threat to a patient's life or vital functions. For example, nausea which persists for several hours may be considered severe nausea, but may not be considered an SAE. On the other hand, a stroke which results in only a limited degree of disability may be considered only a mild stroke, but would be considered an SAE. Severity and seriousness should be independently assessed when recording AEs on the eCRF and SAEs on the SAE Report Form.

11.1.3 Adverse Reaction

An adverse reaction (AR) means any adverse event caused by a drug. Adverse reactions are a subset of all suspected adverse reactions where there is a reason to conclude that the drug caused the event.

11.1.4 Suspected Adverse Reaction

Suspected adverse reaction (SAR) means any adverse event for which there is a reasonable possibility that the drug caused the adverse event. Reasonable possibility means that there is evidence to suggest a causal relationship between the drug and the adverse event. An SAR implies a lesser degree of certainty about causality than adverse reaction, which means any adverse event caused by a drug.

11.1.5 Recording and Reporting of Adverse Events

Recording of Adverse Events

All AEs of any patient during the course of the research study will be recorded in the eCRF, and the investigator will give his or her opinion as to the relationship of the AE to the study drug treatment (i.e., whether the event is related or unrelated to study drug administration).

All AEs should be documented. A description of the event, including its date of onset and resolution, whether it constitutes a serious adverse event (SAE) or not, any action taken (e.g., changes to study treatment), and outcome, should be provided, along with the investigator's assessment of causality (i.e., the relationship to the study treatment[s]). For an AE to be a suspected treatment-related event there should be at least a reasonable possibility of a causal relationship between the protocol treatment and the AE. Adverse events will be graded according to the NCI CTCAE v4.03, and changes will be documented.

If the AE is serious, it should be reported immediately to SCRI Innovations SD. Other untoward events occurring in the framework of a clinical study are to be recorded as AEs (i.e., AEs that occur prior to assignment of study treatment that are related to a protocol-mandated intervention, including invasive procedures such as biopsies, medication washout, or no treatment run-in).

CONFIDENTIAL

STUDY DRUG(S): CARFILZOMIB AMENDMENT 2 DATE: 25 FEBRUARY 2015

Any clinically significant signs and symptoms; abnormal test findings; changes in physical examination; hypersensitivity; and other measurements that occur will be reported as an AE, and collected on the relevant eCRF screen.

Test findings will be reported as an AE if: the test result requires an adjustment in the study drug(s) or discontinuation of treatment, and/ or test findings require additional testing or surgical intervention, a test result or finding is associated with accompanying symptoms, or a test result is considered to be an AE by the investigator.

Reporting Period for Adverse Events

All AEs regardless of seriousness or relationship to carfilzomib treatment (called study treatment), spanning from the start of study treatment, until 30 calendar days after discontinuation or completion of study treatment as defined by the clinical study for that patient, are to be recorded on the corresponding screen(s) included in the eCRF.

All AEs resulting in discontinuation from the study should be followed until resolution or stabilization. All new AEs occurring during this period must be reported and followed until resolution unless, in the opinion of the investigator, the AE or laboratory abnormality/ies are not likely to improve because of the underlying disease. In this case, the investigators must record his or her reasoning for this decision in the patient's medical record and as a comment on the eCRF screen.

After 30 days of completion of protocol-specific treatment or discontinuation, only AEs, SAEs, or deaths assessed by the investigator as treatment related are to be reported.

